## **Funding**

Pasteur Institute of Iran, Tehran, Iran

## **Sponsor**

Pasteur Institute of Iran

## Background

At the end of December 2019, China reported several pneumonia cases of unknown aetiology in Wuhan. The disease caused by Severe Acute Respiratory Syndrome Coronavirus 2 (SARS-CoV-2), a member of the coronaviridae family, was named COVID-19 and made a rapidly growing epidemic throughout the world, reaching 186 countries to date.

SARS-CoV-2 has four structural proteins: spike (S), envelope (E), membrane (M), and nucleocapsid (N). Protein S mediates the virus entry to the host cell through its Receptor-Binding Domain (RBD) attachment to the host cell receptor (ACE2) and therefore is the target of neutralizing antibodies. These features make the RBD a good candidate for S-protein-based COVID-19 vaccines.

The Finlay Vaccine Institute, a leader in Cuban health technology, designed the FINLAY-FR-2 (SOBERANA 02) vaccine for emergency use against SARS-CoV-2. This vaccine contains an injectable suspension containing the S protein's receptor-binding domain (RBD), conjugated to tetanus toxoid and adsorbed on aluminum hydroxide gel.

Finlay Institute has recruited this conjugation technology to produce various vaccines like the *Haemophilus influenzae* type B vaccine (Quimi-Hib) within the past 15 years.

Conjugate vaccines can induce a robust immune response against bacterial infections like *Haemophilus influenzae*, *Neisseria meningitidis*, and *Streptococcus pneumoniae* by linking bacterial polysaccharides to a carrier protein. The immune system normally recognizes polysaccharide chains as T-independent (TI) antigens, which means B-cell proliferation and antibody secretion happen in the absence of T cells. The conjugated bacterial polysaccharides - carrier proteins, *deceive the immune system into identifying the complex as a T-dependent antigen which means the induction of B-cell proliferation requires T-cell help*. As a result, a long-lasting immune response will be obtained by forming memory B and T cells. Compared with unconjugated vaccines, IgG antibodies are more produced and have higher avidity to the conjugate antigen, representing a longer immunity against bacterial infection. In addition,

children < 2 years are non-responsive to most unconjugated vaccines due to their immature immune systems; however, conjugate vaccines are highly effective in this group of age.

Additionally, unconjugated polysaccharide-based vaccines require approximately 5-10 times more antigens than their conjugated counterparts to reach the determined immunity, so conjugate vaccines are probably less reactogenic due to their lower antigen levels.

Preclinical evaluations of the SOBERANA-02 vaccine in animals showed immunogenicity, high anti-RBD IgG antibody titers, and blocked RBD/ACE2 interaction. Furthermore, Repeat-dose toxicity studies showed safety, tolerability and no toxicity.

Phases 1 and 2 of the study in Cuba also showed these vaccine candidates' safety, reactogenicity, and immunogenicity. We will conduct a randomized, double-blind, placebo-controlled phase 3 trial of Soberna-02 and SOBERANA Plus (products manufactured by Finlay Institute of Cuba) to evaluate the efficacy and safety of these candidates in Iranian adults.

## **Objectives**

### **1. Primary Objectives**

- o To determine the efficacy of protein conjugated vaccine/ protein conjugated vaccine + third dose to prevent symptomatic COVID-19 in 18–80-year-old Iranians.

### **2. Secondary Objectives**

- o To determine the efficacy of protein conjugated vaccine/ protein conjugated vaccine + third dose to prevent severe forms of COVID-19 in 18–80-year-old Iranians.
- o To determine the efficacy of protein conjugated vaccine/ protein conjugated vaccine + third dose to prevent COVID-19-related death in 18–80-year-old Iranians.
- o To determine the immunogenicity of protein conjugated vaccine/ protein conjugated vaccine + third dose in the 18–80-year-old Iranians.
- o To determine the safety of protein conjugated vaccine/ protein conjugated vaccine + third dose in 18–80-year-old Iranians.

# Methods

## 1. Study Design

### 1.1. Overall Design

This study is a multicentric, randomized, double-blind, placebo-controlled phase-3 trial to evaluate the efficacy, safety, and immunogenicity of the SOBERANA-02 (25µg) and SOBERANA Plus (50µg) in healthy adults or adults with stable underlying diseases.

The study consists of two cohorts to evaluate the efficacy, immunogenicity and safety of two vaccination regimens:

- Cohort 1: covers a 2-dose schedule of SOBERANA-02 (25µg), 28 days apart
- Cohort 2: as a 3dose schedule (2 doses of SOBERANA-02 [25µg] plus the third dose of SOBERANA-plus) 28 days apart

### 1.2 Justification for Injection of Doses on days 0, 28 and 56

The injection scheme is determined based on preclinical studies on animals. Knowing the immune system performance usually for vaccines based on prime-boost strategy, the interval between the two doses is at least three weeks. For example, the interval between two doses of Pfizer, Moderna, AstraZeneca, and Sputnik V is 21, 28, 28, and 21 days, respectively. For the SOBERANA candidate vaccine, the interval between doses is also set at 28 days.

## 2. Study population

### 2.1 Number of participants

The estimated sample size is 24,000 (allocation ratio of 4:1 for vaccine vs. placebo groups).

- The C1 cohort includes 18,000 volunteers who will receive two doses of SOBERANA-02 on days 0 and 28 in 6 cities (Bandar Abbas, Kerman, Isfahan, Hamadan, Babol, and Sari)
- The C2 cohort includes 6,000 volunteers who will receive two doses of SOBERANA-02 (days 0 & 28) plus a third dose of SOBERANA-plus on day 56 in two cities (Zanjan and Yazd)

The selected areas based on the number of doses and laboratory assays are detailed in Box 1.

### 2.2 Inclusion Criteria

- Male or female aged 18 -80 years old

- o Participants who can follow vaccination schedules, visits, laboratory tests and other study procedures.
- o Participants with healthy conditions or/with a controlled medical condition(s) that is under control.
- o Having Iranian nationality
- o Residents of the cities of the study

### **2.3 Exclusion Criteria**

- o Previous receipt of any COVID-19 vaccines
- o Current clinically or lab-confirmed COVID-19 at the time of enrolment
- o History of tetanus toxoid vaccination within three months before the current study
- o Pregnant or breast-feeding women or those who intend to get pregnant within three months after the last vaccine shot
- o History of receiving blood or its products such as immunoglobulin within the past three months
- o Uncontrolled hypertension (systolic blood pressure >140 mmHg, or diastolic blood pressure > 90 mmHg)
- o Type 2 diabetes mellitus (HbA1C > 7.5%)
- o Chronic renal disease (GFR < 30 CC/min)
- o Chronic liver disease (AST ≥ 100 U/L, ALT ≥ 150 U/L)
- o Uncontrolled asthma (asthmatic attack within the past three months)
- o Severe allergic reaction to any vaccines (anaphylaxis)
- o Cigarette smoking (more than 20 per day for more than 20 years)
- o Contraindication for muscular injections due to coagulation disorders
- o Mental diseases
- o Any coagulation disorders that contraindicate intramuscular injections
- o Using immunosuppressive medicines like nasal and oral steroids (topical steroids are not exclusion criteria), cytostatic agents, interferon, immunoferron, transfer factor, Biomodulin T, Gamma globulin, Levamisole, Heberferon, Thymosin, and other immunomodulatory drugs since one month before vaccination
- o Fever or any acute infectious disease within seven days before vaccination
- o Tattoos on the deltoid muscle of both arms.

- Those in phase 1 of the national plan for establishing and expanding COVID-19 vaccination.

## Note

Up to 30% of volunteers with the following conditions can enter the study:

- Obesity (BMI >30 kg/m^2)
- Controlled hypertension (both self-declared and on-site systolic blood pressure <140 mmHg and diastolic pressure < 90 mmHg, the volunteer will be included in the study despite using antihypertensive drugs)
- Chronic renal disease (based on the lab test result in the past six months): GFR: 30-60 CC/min; GFR < 60 will not be included in the study.
- Chronic liver disease that is < 5 folds to the normal range (based on the lab test results in the past six months): AST < 100 U/L, ALT < 150 U/L
- Type 2 diabetes mellitus (based on the lab test result in the past six months): HbA1C < 7.5
- Chronic obstructive pulmonary disease (COPD)
- Controlled asthma (no asthmatic attack in the past three months)
- A history of any malignancy or cancer
- Ischemic heart disease

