## 2.4 Criteria to Prohibit the Second/Third Dose During the Study (Exit criteria):

- A diagnosis of COVID-19 with PCR test after the last dose of injection
- Severe fever (axillary temperature ≥ 38°C) for three days or allergic reaction to the previous dose of the vaccine
- SAEs following the previous shot
- Vaccination with diphtheria/tetanus vaccine between the two doses of the candidate vaccine
- Volunteer being pregnant

---

 Based on the national plan to establish and expand COVID-19 vaccination, everyone in phase 1 of vaccination priority will receive the vaccine in the next few weeks. These individuals are ineligible to participate in this study if they are in the following groups: All employees who provide first-line care to COVID-19 patients at high risk of contracting and transmitting the infection, including healthcare personnel in both the public and private sectors, the country's laboratory, faculty and staff of universities as well as the Ministry of Health, Treatment and Medical Education; People at risk of hospitalization and death due to COVID-19, including nursing home residents and nursing home staff, Veterans esp. veterans over 50% and chemical respiratory veterans living in veterans' care centers, and mentally and physically disabled people living in these centers.

A restriction applies to health workers currently in the first phase of national vaccination priorities, despite receiving general vaccinations with approved vaccines. If they wish to enroll in this trial and enter the study, there is a prohibition against it.

- A diagnosis of COVID-19 with PCR test after the last dose of injection Severe fever (axillary temperature  $\geq 38^{\circ}\text{C}$ ) for three days or severe allergic reaction (anaphylaxis) to the previous dose of the vaccine
- Receiving drugs affecting the immune system between two doses of the vaccine
- Any disease that affects a candidate's immunity level between two injections, based on the diagnosis of a medical professional

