### **3.1 Patient Recruitment**

**3.1.1 First stage:** We will invite the public via social networks, text messages, and media. Our trained staff will define the objectives of the study and inclusion criteria for participants and make sure that everyone understands them. Further information will be available on the recruiting website. Participants can register on the website after assessing the eligibility criteria. The required registration items will be the city name, national ID number, phone number, and history of underlying disease(s). Healthy people with chronic conditions that are under control (diabetes, liver or renal disease, and hypertension) can participate in the study after a complete examination by the study physician and laboratory results in the following range:

- Chronic renal disease (GFR > 30 CC/min calculated based on the blood creatinine level)
- Chronic liver disease (AST < 100 U/L, ALT < 150 U/L)
- Type 2 diabetes mellitus (HbA1C < 7.5%)
- Hypertension (Systolic blood pressure < 140 mmHg and diastolic blood pressure < 90 mmHg on medication based on self-declaration and on-site vital sign assessment)

**3.1.2 Second stage:** The eligible volunteers will receive preliminary approval by a text message containing the appointment date, time, and address of the vaccination

**3.1.3 Third stage (visit 1):** In case of any ambiguity about the situation, volunteers can ask further questions from research physicians.

After taking the informed consent in two copies, the physician will examine the volunteers and order further screening or laboratory analyses. All consenting participants will be screened for underlying chronic conditions and COVID-19-related clinical symptoms. Then volunteers will receive a unique randomization ID that helps them to check their vaccination status until the end of the study.

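### The renal line in the Note under 2.3 admits and bars the same GFR range, and 2.4 carries two thresholds for one allergic-reaction criterion

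*Protocol*

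**What the plan says.** **Renal function.** The Protocol sets a GFR limit in three places.

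- Section 2.3 (Exclusion Criteria) excludes "Chronic renal disease (GFR < 30 CC/min").
- The Note that follows 2.3, which lists conditions allowed for up to 30% of volunteers, gives chronic renal disease as "GFR: 30-60 CC/min; GFR < 60 will not be included in the study".
- Section 3.1.1 (Patient Recruitment, first stage) lists the laboratory range for participation as "Chronic renal disease (GFR > 30 CC/min calculated based on the blood creatinine level").

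**Next dose after an allergic reaction.** Section 2.4 lists the criteria that prohibit the second or third dose. One bullet joins severe fever to an allergic reaction: "for three days or allergic reaction to the previous dose of the vaccine". A later bullet under the same heading repeats the criterion with a severity qualifier: "for three days or severe allergic reaction (anaphylaxis) to the previous dose of the vaccine". That later bullet also repeats the criterion on a PCR diagnosis of COVID-19 and runs it into the fever and allergy text without a break.

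**The concern.** These are operative rules: site physicians use them to decide who is enrolled and who is injected again. In the renal line, the same person is acceptable and unacceptable within one sentence. A physician with a volunteer in the 30 to 60 range can cite the Protocol for either decision. In 2.4, a physician facing a non-anaphylactic allergic reaction finds one bullet that is met and a second version of it that is not, with nothing to say whether the second was meant to replace the first.

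Participant safety is at stake first. There is also a narrower analysis question. Section 6.2.2 defines the immunogenicity population by receipt of every dose, so the rule that decides who gets the next dose also helps to decide who is in that set.

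**Working it through.** No formula applies, and the Protocol states no figure to reproduce. The check sets the passages side by side.

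**Renal rule.** The inputs are the limits in 2.3 (excluded below 30), 3.1.1 (accepted above 30) and the two halves of the Note's line (30 to 60 admitted; below 60 refused).

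| GFR (cc/min) | 2.3 | 3.1.1 | Note, first half | Note, second half |
|---|---|---|---|---|
| 25 | excluded | outside accepted range | outside admitted range | refused |
| 30 | not excluded | outside accepted range | admitted | refused |
| 45 | not excluded | accepted | admitted | refused |
| 60 | not excluded | accepted | admitted | not refused |

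1. The admitted set in the Note is 30 ≤ GFR ≤ 60, and the refused set is GFR < 60. Their overlap is 30 ≤ GFR < 60.
2. Only a GFR of exactly 60 lies in the admitted set and outside the refused set. The second half therefore cancels almost all of the first.
3. At GFR 45, sections 2.3 and 3.1.1 both let the volunteer in, while the Note both admits and refuses.
4. At GFR exactly 30, section 2.3 does not exclude and the Note's first half admits, but 3.1.1 requires a value above 30. This boundary mismatch would remain even if the Note's second half were removed.

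**Allergic-reaction criterion.** The inputs are the two bullets in 2.4.

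| Event after the previous dose | Broader bullet | Narrower bullet |
|---|---|---|
| Anaphylaxis | prohibits next dose | prohibits next dose |
| Non-anaphylactic allergic reaction | prohibits next dose | not met |

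1. Section 2.4 lists criteria that each prohibit a further dose. It does not require all of them to be met, and no bullet instructs a site to continue.
2. Read that way, a non-anaphylactic reaction meets the broader bullet, and that is enough to prohibit the dose.
3. The narrower bullet then adds no case that the broader one misses, so its severity qualifier has no effect.
4. A qualifier with no effect, in a bullet that otherwise repeats an earlier one, suggests that two versions of one list were left in place. The current text does not say which was intended.

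**The case against.** **On the renal line.** It can be said that this is a one-number slip: 2.3, 3.1.1 and the lower end of the Note's own range all use 30, and only the trailing clause disagrees. That is plausible, but the Protocol does not say so, and the clause as written is an eligibility rule. It is also fair that eligibility is judged by a physician and recorded in an eCRF on one common platform (3.1.3, 3.2.2, 6.5). The documents do not show how that platform applies the GFR rule, so it is not established that sites will in fact differ; the text only leaves them free to.

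**On the allergy criterion.** A reader might infer that the two bullets contradict each other outright, so that a participant is stopped under one and continued under the other. The text does not support that. Failing to meet the narrower bullet is not permission to dose, and the literal list gives a single answer. What stands is that two thresholds for one rule are both current text. The amendment table shows the narrower wording as a revision of the broader, so a site aware of that could follow the narrower one alone. The point does not rest on that table, since both versions appear in the body of 2.4.

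**On the analysis.** A reader might also infer that the efficacy comparison is compromised. It is not shown to be. Eligibility is settled before randomisation and blocks are allocated within each city (3.2.1), so uneven renal enrolment between cities would alter case mix but not bias the vaccine-placebo comparison within a city. Efficacy is analysed by ITT (6.2.1). Withholding a dose changes who completes the regimen, but it does not remove anyone from the group to which they were randomised.

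**Conclusion.** The renal line is a strict self-contradiction in current text. It covers every volunteer with chronic renal disease and a GFR from 30 up to, but not including, 60, and there is a separate mismatch with 3.1.1 at exactly 30. The allergic-reaction point is weaker: it is a duplicated criterion with two thresholds, and its intended scope is unclear only for non-anaphylactic reactions.

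The size in participants cannot be given. The Protocol states neither the share of volunteers with a GFR of 30 to 60 nor a rate of non-severe allergic reaction, and any head count would simply restate an assumed rate. The consequence is uncertainty over eligibility and re-dosing, and possibly over who enters the immunogenicity set under 6.2.2. No sample-size, power or ITT efficacy figure depends on either point.

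The conclusion assumes only that 2.4 is a list in which any one criterion suffices. If a site instead read the later bullet as replacing the earlier, the ambiguity would matter more. The point merits correction because it bears on safety and is cheap to settle, not because it alters the statistical design.

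**What to change.** The sponsor and the safety physicians should do two things.

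1. Reconcile the GFR statements in 2.3, the Note and 3.1.1 into one rule, worded identically in all three places and explicit about the boundary value.
2. State the allergic-reaction criterion once in 2.4, remove the duplicate bullet (including the repeated PCR item), and separate the merged criteria.

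Which GFR limit and which reaction threshold apply is a clinical decision for them, and this review proposes neither. Checking that the eCRF at all eight sites reflects the reconciled wording would be a sensible accompaniment.

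The cost is a short wording amendment and, where needed, a change to a data check. No sample size or analysis method has to change.

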## 2.4 Criteria to Prohibit the Second/Third Dose During the Study (Exit criteria):

- A diagnosis of COVID-19 with PCR test after the last dose of injection
- Severe fever (axillary temperature ≥ 38°C) for three days or allergic reaction to the previous dose of the vaccine
- SAEs following the previous shot
- Vaccination with diphtheria/tetanus vaccine between the two doses of the candidate vaccine
- Volunteer being pregnant

---

 Based on the national plan to establish and expand COVID-19 vaccination, everyone in phase 1 of vaccination priority will receive the vaccine in the next few weeks. These individuals are ineligible to participate in this study if they are in the following groups: All employees who provide first-line care to COVID-19 patients at high risk of contracting and transmitting the infection, including healthcare personnel in both the public and private sectors, the country's laboratory, faculty and staff of universities as well as the Ministry of Health, Treatment and Medical Education; People at risk of hospitalization and death due to COVID-19, including nursing home residents and nursing home staff, Veterans esp. veterans over 50% and chemical respiratory veterans living in veterans' care centers, and mentally and physically disabled people living in these centers.

A restriction applies to health workers currently in the first phase of national vaccination priorities, despite receiving general vaccinations with approved vaccines. If they wish to enroll in this trial and enter the study, there is a prohibition against it.

- A diagnosis of COVID-19 with PCR test after the last dose of injection Severe fever (axillary temperature  $\geq 38^{\circ}\text{C}$ ) for three days or severe allergic reaction (anaphylaxis) to the previous dose of the vaccine
- Receiving drugs affecting the immune system between two doses of the vaccine
- Any disease that affects a candidate's immunity level between two injections, based on the diagnosis of a medical professional

